22. CHANGES TO PATIENT ENTRY CRITERIA

Not applicable.

APPENDIX 1. DEFINITIONS

Relapse (attack)

A relapse will be defined as the appearance of one or more new neurological abnormalities or the reappearance of one or more previously observed neurological abnormalities.

This change in clinical state must last at least 48 hours and be immediately preceded by an improving neurological state of at least thirty (30) days from onset of previous relapse.

This criterion is different from the clinical definition of relapse: "at least 24 hours duration of symptoms"ⁿ. Since "in study" relapse definition must be supported by an objective neurological evaluation (see next paragraph), a neurological deficit must sustain long enough to eliminate pseudo-relapses.

An event will be counted as a relapse only when the subject's symptoms are accompanied by observed objective neurological changes, consistent with at least one of the following:

- an increase of at least 0.5 in the EDSS score as compared to previous evaluation.
- an increase of one grade in the score of 2 or more of the 7 FS as compared to previous evaluation.
- an increase of 2 grades in the score of one FS as compared to the previous evaluation.

The EDSS/FS/AI (in the first visit indicative for a relapse, as well as in follow up visits) will be a part of a complete neurological assessment performed by the Examining Neurologist/ Physician (or the Study's Neurologist/ Physician, in case all subjects are in the LAQ/5063 open label phase).

The subject must not be undergoing any acute metabolic changes such as fever or other medical abnormality. A change in bowel/bladder function or in cognitive function must not be entirely responsible for the confirmation of a relapse.

[figure not shown]
ⁿ Guidelines from the International Panel on the Diagnosis of Multiple Sclerosis (McDonald, Ann. Neurol. 2001;50:121-127)

EVALUATION & CONFIRMATION OF A RELAPSE IN THE STUDY

General Instructions

To the Subject: Contact the site upon any neurological change which is suspected as a relapse. This should be done <48 hours after start of symptoms.

To the Site: 1) try to get an accurate as possible estimation of the symptoms onset date from the subject (should be More than 48h but less than 1 week after onset), 2) Invite the subject for a visit, 3) Make sure that Treating & Examining Physicians* are available.

* or Study Physician, where applicable

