The following will be performed at the Termination visit of LAQ/5063 active double-blind phase (completion of the full 36 weeks or as requested by the Sponsor), and/or at any early discontinuation visit occurring as long as the Sponsor continues the development of laquinimod 0.6 mg for RRMS:

- Vital signs, including weight
- Complete physical examination
- Record of AEs: If an AE is still ongoing, or a new AE is present at the termination visit, it will be followed according to the discretion of the Investigator and recorded in the subject's source documents and in the CRF (see Section 7.3.4).
- IMP accountability
- Subject compliance
- Review concomitant medication. Note: moderate/strong CYP3A4 inhibitors are disallowed during the 30 days after the last dose has been administered. For information on the use of CYP1A2 substrates following laquinimod cessation, please refer to the laquinimod IB.

- ECG
- Complete neurological examination, including FS, AI, and EDSS, and 25 foot walk test
- MSFC (this is relevant for LAQ/5063 active double-blind phase only)
- Evaluation of relapses (if applicable). If a relapse is confirmed or ongoing at the termination visit, it will be followed until relapse stabilization. All follow-up evaluations must be documented in the source documents and the CRF.
- Laboratory tests
 - Hematology
 - Serum chemistry (including GFR estimation)
 - Serum pregnancy test (β -hCG) for women of child-bearing potential
 - Blood sampling for PK study (ancillary study in sub-group of subjects. For subjects participating in this study, the IMP will be administered at the site. This is relevant for LAQ/5063 active double-blind phase only)
 - Blood sampling for PPK study (ancillary study in all subjects). (This is relevant for LAQ/5063 active double-blind phase only)
 - For a detailed sampling plan for PK and PPK studies refer to Section 8.4. (This is relevant for LAQ/5063 active double-blind phase only)
- For all subjects who are female of child-bearing potential:
 - The use of effective contraception will be ascertained (should be recorded in the source documents) and all subjects will be reminded to continue using two acceptable methods of contraception up to 30 days from the date of the last dose of the IMP
 - Subjects will be instructed about the potential teratogenicity and delayed risks for a child exposed in uterus to laquinimod

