7.3.7. Visits during Relapses (Scheduled and Unscheduled)

Subjects will be instructed to contact their study site immediately should any symptoms suggestive of a relapse occur (see Section [8.1.4](#)).

The Study Neurologist/Physician will evaluate the subject within 7 days of the telephone contact, conditional upon a symptomatic period of ≥ 48 hours.

The relapse assessment will be documented in the source documents and in the CRF accordingly. A complete neurological assessment, including FS, AI and EDSS, will be performed by the Study Neurologist/Physician.

The decision as to whether the neurological change is considered a relapse will be made by the Study Neurologist/Physician based on the criteria listed in [Appendix 1](#).

Corticosteroids therapy (as described in Section [6.1](#)) may be given for a confirmed relapse at the discretion of the Treating Neurologist/Physician and must be recorded in the CRF.

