8.1.4. On-Study Relapse Evaluation Procedures

The subject will be examined within 7 days of the telephone contact, conditional upon a symptomatic period of \geq 48 hours.

For the open-label phase (LAQ/5063 OL) only one neurologist/physician is required (Study Neurologist/Physician) to perform a neurological examination and treat the subject as needed.

Relapse Determination

The Study Neurologist/Physician will make the decision as to whether the neurological change is considered a relapse, based on EDSS/FS scores (see Relapse Definition, [Appendix 1](#)).

Follow-up visits to monitor the course of the relapse will be made at the Study Neurologist/Physician discretion, in addition to the assessment at the next scheduled visit.

In the case of an ongoing or just-started relapse at the study termination visit (Week 36)/early discontinuation visit, subjects will be followed up until the end of the relapse, wherever possible (see Section [7.3.3](#)).

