11. STATISTICAL METHODOLOGY

A total of up to 264 subjects, randomized to treatment with 0.3 mg or 0.6 mg of laquinimod, are expected to be recruited into this double-blind, multi-national trial. The trial is planned for 36 weeks of double-blind treatment.

All data summaries in this trial will be presented by treatment group.

The statistical analyses of this study will be exploratory in nature. Continuous variables will be presented by descriptive statistics (mean, standard deviation, minimum, median and maximum values), by treatment group. For categorical variables treatment group counts and percentage from total subject population will be tabulated.

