11.4.6. The total number of confirmed relapses

Descriptive statistics of the total number of confirmed relapses will be presented by treatment group.

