11.4.7. The proportion of relapse-free subjects

A subject that did not experience any relapse during the treatment period will be considered as a responder for the purpose of this analysis.

The counts and percentages of relapse-free subjects will be presented by treatment group.

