3. Subjects must be in a stable neurological condition, relapse-free and free of any corticosteroid treatment [intravenous (IV), intramuscular (IM) and/or per os (PO)] or adrenocorticotropic hormone (ACTH), 60 days prior to re-enrollment.
4. Women of child-bearing potential (for example women who are not postmenopausal or surgically sterilized) must practice an acceptable method of birth control for 30 days before taking the study drug and two acceptable methods of birth control during the study and up to 30 days after the last dose of the study treatment was administered. Acceptable methods of birth control in this open label extension phase include: intrauterine devices, barrier methods (condom or diaphragm with spermicide) and hormonal methods of birth control (e.g. oral contraceptive, contraceptive patch, long-acting injectable contraceptive).
5. Subjects must be willing and able to comply with the protocol requirements for the duration of the study.
6. Subjects must be able to comprehend, sign and date a written informed consent prior to re-enrolling into the LAQ/5063 OL study.

Exclusion Criteria for returning subjects

Any of the following conditions will exclude the subject from re-enrolling into the study:

1. Premature discontinuation from the LAQ/5063 OL study, for any reason, except planned pregnancy.
2. Subjects with progressive forms of MS or other non RRMS variant of neuroinflammatory or demyelinating diseases.
3. Use of experimental or investigational drugs and/or participation in drug clinical studies within 6 months prior to re-enrollment visit.
4. Use of immunosuppressive agents, or cytotoxic agents, including cyclophosphamide and azatioprine within 12 months prior to re-enrollment visit.
5. Use of either of the following within 2 years prior to re-enrollment: natalizumab (Tysabri®), rituximab, ocrelizumab, atacicept, belimumab, or ofatumumab.
6. Previous treatment with glatiramer acetate (Copaxone®), IFN-β (either 1a or 1b), fingolimod (Gilenya®), dimethyl fumarate (Tecfidera) or IV immunoglobulin (IVIG) within 2 months prior to re-enrollment visit.
7. Use of teriflunomide (Aubagio®) within- 2 years prior to re-enrollment, except if active washout (with either cholestyramine or activated charcoal) was done 2 months or more prior to randomization.
8. Use of mitoxantrone (Novantrone) within 5 years prior to re-enrollment in subjects with normal ejection fraction and who did not exceed the total lifetime maximal dose.

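### As worded, the relapse definition requires an improving state beforehand; read literally, it leaves out a new attack in a subject who has been stable

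*Combined protocol and SAP*

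**What the plan says.** Appendix 1 opens broadly: a relapse is one or more new or returning neurological abnormalities. It then adds conditions. The change must last at least 48 hours and must also "be immediately preceded by an improving neurological state of at least thirty (30) days from onset of previous relapse". A further paragraph requires an objective change in EDSS or Functional System scores before an event is counted.

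The definition is operative. Section 7.3.7 says that the decision on whether a neurological change is a relapse "will be made by the Study Neurologist/Physician based on the criteria listed in" Appendix 1. Section 8.1.4 says that the decision rests on EDSS and Functional System scores, and it too points to Appendix 1.

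The Synopsis and Section 4.1.3 list relapse rate and the proportion of relapse-free subjects as efficacy outcomes, with no limit to one study phase. Section 11.4.6 states: "Descriptive statistics of the total number of confirmed relapses will be presented by treatment group". Section 11.4.7 states: "A subject that did not experience any relapse during the treatment period will be considered as a responder". On the analysis as a whole, Section 11 says: "The statistical analyses of this study will be exploratory in nature".

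**The concern.** The preceding-state condition is mandatory and names one state only. Many subjects with relapsing-remitting disease will be neither improving nor worsening between attacks. If such a subject has a new attack with the required EDSS or Functional System change, the written rule still fails, because the state just before it was stable and not improving.

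The clause is also tied to a previous relapse, and it does not say what applies when a subject has had none on study.

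At stake are the two relapse outcomes. A neurologist who follows the text exactly records fewer relapses and more relapse-free subjects. A neurologist who reads it as a spacing rule counts the same events as relapses. The outcome would then depend partly on how each site reads one sentence.

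**Working it through.** The plan states no relapse rate, power or sample size that depends on this clause, so there is no figure to reproduce. The check is a comparison of texts.

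**1. Is the condition really necessary?** Yes. It is joined by 'and' to the 48-hour requirement under the same 'must'. The EDSS and Functional System criteria come afterwards as a further necessary condition, so meeting them does not replace it.

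**2. Does another section supply a stable alternative?** Not in the visible text. Sections 7.3.7 and 8.1.4 both refer back to Appendix 1 and give no preceding-state rule of their own.

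**3. Does the protocol treat stability as a separate state?** Yes, in two places.
- Appendix 10, inclusion criteria for returning subjects: "Subjects must be in a stable neurological condition, relapse-free and free of any corticosteroid treatment", for 60 days before re-enrollment. Under the literal rule, an attack soon after re-enrollment follows a state that the protocol itself calls stable.
- Section 8.1.4 says that for a relapse present at termination, "subjects will be followed up until the end of the relapse, wherever possible", and it cross-refers to Section 7.3.3, which says: "If a relapse is confirmed or ongoing at the termination visit, it will be followed until relapse stabilization". This is weaker support, since it concerns when follow-up stops.

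**4. How do the two readings classify events?** Assume that the 48-hour and objective criteria are met in every row.

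| State before the new event | Literal reading | 30-day separation reading |
|---|---|---|
| Improving, at least 30 days after last onset | Counted | Counted |
| Stable, at least 30 days after last onset | Not counted | Counted |
| Stable, no previous on-study relapse | Not counted; the 30-day part is undefined | Counted, as there is nothing to separate from |
| Less than 30 days after last onset | Not counted | Not counted |

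The readings part in the second and third rows.

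**5. Direction and size.** Let k be the number of attacks in those two rows that sites leave out, m the number of subjects whose only attacks are among them, and N the denominator. The relapse count falls by k and the relapse-free proportion rises by m/N. The second effect assumes that Section 11.4.7 uses the Appendix 1 definition, which it does not state. The documents give neither k nor m, and they specify no N for an open-label relapse table. If all sites apply the separation reading, k = m = 0.

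**6. Can the data show an improving state?** Hardly. After Month 24, scheduled neurological examinations are six months apart (Section 8.1.2), and extra visits during a relapse are discretionary (Section 8.1.4). Scheduled visits cannot establish the course over the preceding 30 days, so sites have to interpret the clause.

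**The case against.** The strongest reply is that the literal reading defeats itself. The 30 days begin at onset of an attack, when the subject is by definition getting worse, so nobody can have been improving throughout. The sensible meaning is a minimum gap between attacks, and a stable subject satisfies that. This stands as evidence of intent, and it is why the practical effect may be nil. It also shows that the sentence does not say what was meant, and the sentence is what the neurologist is told to apply.

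The Appendix 1 figure is not shown and might carry operational detail. That is a fair limit, but it cannot be assumed to override a written mandatory criterion.

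The supporting sections are not counting rules. The returning-subject criterion covers only women coming back after a planned pregnancy, case by case, and Section 7.3.3 concerns follow-up. This is correct: they show that stability is a recognised state, and no more than that.

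A new wording late in the study breaks the series, and a note confirming the separation reading might do as well. The first part is a real cost. A note would help, but it would leave the contradictory clause in place as the criterion that Sections 7.3.7 and 8.1.4 cite.

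Finally, a change to the definition is not confined to outcome counting. Section 7.3.7 allows corticosteroids for a confirmed relapse, and Section 6.2 otherwise disallows oral and parenteral steroids. This stands and is carried into the fix.

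**Conclusion.** The clause is worded wrongly for its apparent purpose. Taken as written, it excludes new attacks in stable subjects and leaves a first on-study relapse undefined. The direction is clear: literal use lowers relapse counts and raises the relapse-free proportion, and mixed use makes sites inconsistent. The size cannot be estimated from the documents, and it is zero if all sites already apply a 30-day separation.

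The consequence is limited. The analyses are descriptive, so no test or power is affected. Section 11 is framed on the 36-week double-blind phase, and Appendix 8 confirms that the study is now open label, so only future open-label counts can change. Those still matter: the Synopsis has relapses monitored throughout, and Section 3.5.1 gives the open-label phase an aim of exploring long-term clinical effect.

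A reader might infer that relapses have already been missed, or that the double-blind relapse results are too favourable. The documents do not support that. They do not show how any site applied the clause, and they show no misclassified event. A reader might also want to express the effect as percentage points on the number of ongoing subjects. That would rest on a denominator and event counts that the plan does not supply.

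**What to change.** For outcome counting, reword the Appendix 1 condition to 'a stable or improving neurological state of at least 30 days from onset of any previous relapse', and add a sentence saying that it is met when there is no previous on-study relapse. Apply the new wording prospectively to open-label follow-up, and tabulate relapses before and after the change separately.

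Because Sections 6.2 and 7.3.7 link steroid use to relapse, the sponsor must reconcile those sections with Appendix 1 at the same time. No treatment rule is proposed here.

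The cost is one phrase, one sentence and a split table. The downside is two wordings within one relapse series, which weakens comparison across the change. Double-blind counts are not altered.

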APPENDIX 2. NEUROSTATUS

Standardized Neurological Examination and Assessment of Kurtzke's Functional Systems and Expanded Disability Status

neurostatus

Standardised Neurological Examination and Assessment of Kurtzke's *Functional Systems*¹ and *Expanded Disability Status Scale*¹

SOURCE DOCUMENT

SUBJECT NO/SUBJECT INITIALS

COUNTRY/CENTRE NO

NAME OF EDSS RATER

DATE OF EXAMINATION

¹slightly modified from J. F. Kurtzke, Neurology 1983;33,1444-52
© L. Kappos, Department of Neurology, University Hospitals,
CH-4031 Basel, Version 10/2002

1

NEUROSTATUS**GENERAL GUIDELINES**

To ensure unbiased EDSS assessment in controlled clinical trials, the EDSS rater should not inquire about the patients' condition except as necessary to perform the EDSS assessment.

Patients must be observed to walk the required distance.

NEUROSTATUS (NS)

In the Neurostatus «signs only» is noted when the examination reveals signs of which the patient is unaware.

FUNCTIONAL SYSTEMS (FS)

A score of 1 in the Functional Systems implies that the patient is not aware of the deficit and that the deficit or sign does not interfere with normal daily activities (with the exceptions of optic, vegetative and cerebral functions).

EXPANDED DISABILITY STATUS SCALE (EDSS)

EDSS should not be lower than the highest score of the FS.
Symptoms which are not MS-related will not be taken into consideration for assessments, but should be noted.

2

neurostatus**VISUAL (OPTIC) FUNCTIONS****Definitions****Visual acuity**

The visual acuity score is based upon the line on the Snellen chart at 20 feet (5 m) for which the patient makes no more than one error (use best available correction).

Alternatively best corrected near vision can be assessed but this should be noted and consistently done during follow up.

Fields

0 = normal

1 = signs only, deficits present only on formal testing

2 = moderate, patient aware of deficit, but incomplete hemianopsia on examination

3 = marked, complete homonymous hemianopsia or equivalent

Scotoma

0 = none

1 = small, detectable only on formal (confrontational) testing

2 = large, spontaneously reported by patient

Disc pallor

0 = not present

1 = present

OPTIC FUNCTIONS	OD	OS
Visual acuity (corrected)		
Visual fields		
Scotoma		
Disc pallor		

FUNCTIONAL SYSTEM SCORE	
0	= normal
1	= disc pallor and/or mild scotoma and/or visual acuity of worse eye (corrected) less than 30/30 (1.0) but better than 20/30 (0.67)
2	= worse eye with large scotoma and/or maximal visual acuity (corrected) of 20/30 to 20/59 (0.67–0.34)
3	= worse eye with large scotoma or moderate decrease in fields and/or maximal visual acuity (corrected) of 20/60 to 20/99 (0.33–0.2)
4	= worse eye with marked decrease of fields and/or maximal visual acuity (corrected) of 20/100 to 20/200 (0.1–0.2); grade 3 plus maximal acuity of better eye of 20/60 (0.3) or less
5	= worse eye with maximal visual acuity (corrected) less than 20/200 (0.1); grade 4 plus maximal acuity of better eye of 20/60 (0.3) or less
6	= grade 5 plus maximal visual acuity of better eye of 20/60 (0.3) or less

Definitions

Assessment of impairment/disability

0 = normal

1 = signs only: clinically detectable numbness, facial weakness, or cranial nerve deficit of which patient is not aware

2 = mild: clinically detectable numbness, facial weakness, dysarthria or cranial nerve deficits of which patient is aware

3 = moderate: diplopia with incomplete paralysis of any eye movement, impaired discrimination of sharp/dull in 1 or 2 trigeminal branches, trigeminal neuralgia (at least one attack in the last 24 hours), weakness of eye closure, cannot hear finger rub and/or misses several whispered numbers, obvious dysarthria during ordinary conversation impairing comprehensibility

4 = severe (marked): complete loss of movement of either eye in one direction, impaired discrimination of sharp/dull or complete loss of sensation in the entire distribution of one or both trigeminal nerves, unilateral or bilateral facial palsy with lagophthalmus or difficulty with liquids, sustained difficulty with swallowing, incomprehensible voice

CRANIAL NERVE EXAMINATION

EOM (extra ocular movements) impaired

Nystagmus

Trigeminal damage

Facial weakness

Hearing loss

Dysarthria

Dysphagia

Other bulbar signs

Nystagmus

0 = normal

1 = signs only

2 = gaze evoked nystagmus below limits of "moderate" (usual equivalent is grade one in FS score)

3 = moderate, sustained nystagmus on 30° horizontal or vertical gaze, but not in primary position, patient may or may not realize disturbance (usual equivalent is grade 2 in FS score)

4 = severe, sustained nystagmus in primary position or coarse persistent nystagmus in any direction interfering with visual acuity, complete internuclear ophthalmoplegia with sustained nystagmus of abducting eye, oscillopsia

FUNCTIONAL SYSTEM SCORE

0 = normal

1 = signs only

2a = moderate nystagmus or/and

2b = other mild disability

3a = severe nystagmus or/and

3b = marked extraocular weakness or/and

3c = moderate disability of other cranial nerves

4a = marked dysarthria or/and

4b = other marked disability

5 = inability to swallow or speak

NEUROSTATUS

Definitions

* = optional

REFLEXES

0 = absent, 1 = weak, 2 = normal, 3 = exaggerated, 4 = cloniform,
5 = inexhaustible (indicate difference between R & L by < or >)

Plantar response

0 = flexor, 1 = neutral, 2 = extensor

Cutaneous reflexes

0 = normal, 1 = weak, 2 = absent

*Palmomental reflex

0 = absent, 1 = present

LIMB STRENGTH

The weakest muscle in each group defines the score for that group. Use of functional tests like jumping with one foot, walking on toes or heels are recommended in order to assess grades 3-5 BMRC.

BMRC Rating scale

0 = no activity, 1 = visible contraction without visible joint movement, 2 = visible movements with elimination of gravity, 3 = movements against gravity possible but impaired, 4 = movements against resistance possible but impaired, 5 = normal strength

FUNCTIONAL TESTS

*Position test UE (upper extremities)

Sinking, 0 = none, 1 = mild, 2 = evident

*Position test LE (lower extremities)

Sinking, 0 = none, 1 = mild, 2 = evident

1 = only separate lifting possible (grades from horizontal position in hip joints...°)

2 = even separate lifting not possible

*Walking on heels/tpoies

0 = normal, 1 = impaired, 2 = not possible

*Monopedal hopping

0 = normal, 1 = 6-10 times, 2 = 1-5 times, 3 = not possible

LIMB SPASTICITY

0 = normal, 1 = mild, barely increased muscular tone after rapid flexion of an extremity, 2 = moderate, 3 = severe, barely surmountable increased spastic tonus after rapid flexion of an extremity, 4 = contracted

Gait spasticity

0 = normal, 1 = barely perceptible, 2 = evident, minor interference with function, 3 = permanent shuffling, major interference with function

PYRAMIDAL FUNCTIONS

REFLEXES	R	><	L
Biceps			
Triceps			
Radial			
Knee			
Ankle			
Plantar response			
Cutaneous reflexes			
*Palmomental reflex			

LIMB STRENGTH			
Shoulder			
Elbow flexors			
Elbow extensors			
Hand/finger flexors			
Hand/finger extensors			
Hip flexion			
Knee flexors			
Knee extensors			
Foot/toe flexors			
Foot/toe extensors			
*Position test UE, pronation			
*Position test UE, sinking			
*Position test LE, sinking			
only lifting of single leg possible	o		o
*Walking on heels			
*Walking on tiptoes			
*Hopping on one foot			

SPASTICITY			
Arm			
Leg			
Gait			

FUNCTIONAL SYSTEM SCORE			
0 = normal			
1 = abnormal signs without disability			
2 = minimal disability, patient complains about fatigability in motor tasks and/or BMRC grade 4 in one or two muscle groups			
3a = mild to moderate paraparesis or hemiparesis (usually BMRC grade 4 in more than two muscle groups or BMRC grade 3 in one or two) movements against gravity are possible			
3b = severe monoparesis, refers to BMRC grade 2 or less in one muscle group			
4a = marked paraparesis or hemiparesis (usually BMRC grade 2 in 2 limbs)			
4b = moderate tetraparesis (refers to BMRC grade 3 in 3 or more limbs)			
4c = monoplegia (BMRC grade 0 or 1 in one limb)			
5a = paraplegia, BMRC grade 0 or 1 in all muscle groups of the lower limbs			
5b = hemiplegia			
5c = marked tetraparesis (BMRC grade 2 or less in 3 or more limbs)			
6 = Tetraplegia (grade 0 or 1 in all muscle groups of upper and lower limbs)			

neurostatus**Definitions**

UE = upper extremities

LE = lower extremities

EO = eyes open

EC = eyes closed

Head tremor, rebound

0 = normal

1 = mild abnormality

2 = moderate abnormality

3 = severe abnormality

Truncal ataxia

0 = none

1 = signs only

2 = mild, swaying with EC

3 = moderate, swaying with EO

4 = severe, unable to sit without assistance

Limb ataxia

0 = none

1 = signs only

2 = mild, tremor or clumsy movements seen easily, minor interference with function

3 = moderate, tremor or clumsy movements interfere with function in all spheres

4 = severe, most functions are very difficult

Gait ataxia

0 = none

1 = signs only

2 = mild, abnormal balance only on heel or toe walking, or walking along a line

3 = moderate, abnormal balance on ordinary walking or while seated

4 = severe, unable to walk more than a few steps or requires support by another person or walking aid because of ataxia

Romberg test

0 = normal

1 = mild, mild insecurity with EC

2 = moderate, not stable with EC

3 = severe, not stable with EO

Straight line walking

0 = without problems

1 = impaired

2 = not possible

Note

The presence of severe gait ataxia alone results in a grade of 3 in the cerebellar FS. If weakness interferes with the testing of ataxia, score the patient's actual performance, but also indicate the possible role of weakness by marking the box marked 'X'.

CEREBELLAR FUNCTIONS**CEREBELLAR EXAMINATION**

Head tremor

Truncal ataxia, EO

Truncal ataxia, EC

Tremor/dysmetria UE

Tremor/dysmetria LE

Rapid alternate movements impaired UE

Rapid alternate movements impaired LE

Gait ataxia, EO

Straight line walking, EO

Other, e.g. rebound

Romberg test

R**L****FUNCTIONAL SYSTEM SCORE**

0 = normal

1 = abnormal signs without disability

2 = mild ataxia

3a = moderate truncal ataxia

3b = moderate limb ataxia

4 = severe ataxia in all limbs or trunk

5 = unable to perform coordinated movements due to ataxia

X = weakness (grade 3 or more on pyramidal)
interferes with testing

Definitions

* = optional

UE = upper extremities

LE = lower extremities

Superficial sensation – Touch/pain

0 = normal

1 = signs only, patient is not aware of deficit, but slightly reduced sensation of feeling (temperature, figure writing)

2 = mild, patient is aware of impaired light touch or pain, but able to discriminate sharp/dull

3 = moderate, impaired discrimination of sharp/dull

4 = severe, no discrimination of sharp/dull and/or unable to feel light touch

5 = complete loss, anaesthesia

Vibration sense

0 = normal

1 = mild, graded tuning fork 5–7 of 8 (alternatively) detects more than 10 sec. but less than examiner

2 = moderate, graded tuning fork 1–4 of 8 (alternatively) detects more than 2 sec. but less than 11 sec.

3 = marked, complete loss of vibration sense

Position sense

0 = normal

1 = mild, 1–2 incorrect responses on testing, only distal joints affected

2 = moderate, misses many movements of fingers or toes, proximal joints affected

3 = marked, no perception of movement/astasia

